will review all available safety and PK data collected from the first group of 4 subjects in each cohort. In order to identify the optimum dosage and dosing regimen in each age group, a maximum of 2 dosage/dosing regimen adjustments is assumed in either or both of the Cohorts 3 and 4. Subjects ≥ 6 months to ≤ 36 months of age can be enrolled in Cohort 5 after the completion of Cohort 3 and subjects ≥ 1 month and < 6 months can be enrolled in Cohort 5 after the completion of Cohort 4. Cohort 5 will be opened when either Cohort 3 or 4 is complete. Enrolment in Cohort 5 will continue until 24 evaluable subjects have received RV521 or placebo (2:1). The 4 subjects in the dose group that received the specified dose from each of Cohorts 3 and/or 4 will contribute to this overall total. Thus a minimum of 24 subjects and a maximum of 40 subjects (assuming 2 adjustments per age group) may be enrolled in Part B.

Part C (Multiple Dose, Parallel Group, Cohort 6)

Based on the analysis of the safety, PK, and antiviral data following the completion of Part B, Part C will commence to confirm the antiviral effects of the two dose levels of RV521 vs. placebo. Part C is a double-blind and placebo-controlled study, enrolling 1 cohort (Cohort 6) of up to 111 subjects (≥ 1 month to ≤ 36 months of age). After parent/legal guardian informed consent is obtained, and conditional to satisfactory fulfilment of all inclusion criteria and none of the exclusion criteria subjects will be randomised in a 1:1:1 ratio to receive RV521 at one of two dose levels (RV521 high or low dose) or matching placebo. Subjects will be followed for safety and tolerability, samples will be collected for PK levels, and clinical findings will be collected. Nasopharyngeal swabs will be obtained over the course of the study period to evaluate viral load, presence of other respiratory pathogens and the CCI [REDACTED].

Number of Subjects:

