8.5.4 Method of Assigning Subjects to Treatment Groups

Part A:

Part A of the study is open-label and all subjects will receive RV521. The dose to be received by a given subject will be the dose currently being investigated, at the time the subject is enrolled, in the applicable cohort, as described in [Section 8](#).

Part B and Part C:

In Parts B and C, subjects will be randomised to treatment according to a central randomised list for each cohort. To protect the blind, the list will be produced by an unblinded biostatistician at Syneos Health who will be independent of the blinded statistician.

For Part B, subjects in Cohorts 3 and 4 will be randomised to RV521 or placebo (3:1). The randomisation list for Cohort 5 will be designed to ensure that the subjects who contribute to the final recruitment total of 24 are randomised to receive RV521 or placebo (2:1). The dose to be received by a given subject will be the dose currently being investigated at the time the subject is enrolled, in the applicable cohort, as described in [Section 8.1](#).

For Part C Cohort 6, the randomisation list will be designed such that the total of approximately 111 subjects (37 subjects per treatment group) will be randomised with an aim to have at least 34 evaluable subjects included in the analysis of viral load. Randomisation will be stratified by age

group (≥ 1 month to < 6 months vs. ≥ 6 months to ≤ 36 months) to ensure balance across the treatment groups, but there is no specified number of subjects that will be required in each stratum. Subjects will receive RV521 (age group specific low or high dose level) or placebo in a 1:1:1 ratio. Subjects randomised to placebo will be allocated randomly to either a low dose volume or a high dose volume to maintain the integrity of the double-blind design.

At the time of randomisation, a subject will be sequentially assigned to the next available treatment from the randomisation list for that cohort and stratum. Randomisation will be performed using an interactive web response system (IWRS). A blinded treatment kit (or > 1 kit, if required, in Part B and Part C), corresponding to the randomised treatment, will be allocated to each subject.

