### **Part B**

Part B will be conducted across 3 cohorts (Cohorts 3, 4, and 5) comprising the following age groups:

- Cohort 3:  $\geq$  6 months to  $\leq$  36 months
- Cohort 4:  $\geq$  1 month to  $<$  6 months
- Cohort 5:  $\geq$  1 month to  $\leq$  36 months

After review of the safety and PK data from a specific age group enrolled in Part A, the DSMC will determine the dosage and dosing regimen to be used in that age group in Part B, such that the target group mean trough concentration is approximately equivalent to  $3 \times EC_{90}$ , and approve the start of enrolment in that specified age group, i.e., Cohort 3 can start after Cohort 1 (Part A) has been finalised and Cohort 4 can start after Cohort 2 (Part A) has been finalised. It is anticipated that subjects enrolled in Part B of the study will receive RV521 or placebo twice daily (BID), 12 hours apart, for a period of

This document is confidential.

5 consecutive days (total of 10 doses). However, the dosing regimen may be adjusted depending on the DSMC recommendations.

Groups of 4 subjects will be randomised to receive RV521 or placebo (3:1) in Cohort 3 and Cohort 4, with enrolment occurring in parallel. It is envisioned that data from a group of 4 subjects will be sufficient to confirm the dose exposure relationship for RV521 administered according to a multiple dosing regimen and therefore the DSMC will review all available safety and PK data collected from the first group of 4 subjects in each cohort. In order to identify the optimum dosage and dosing regimen in each age group, a maximum of 2 dosage/dosing regimen adjustments is assumed in either or both of the Cohorts 3 and 4. Subjects  $\geq 6$  months to  $\leq 36$  months of age can be enrolled in Cohort 5 after the completion of Cohort 3 and subjects  $\geq 1$  month and  $< 6$  months can be enrolled after the completion of Cohort 4. Enrolment in Cohort 5 will continue until 24 evaluable subjects have received RV521 or placebo (2:1) at the dosage and dosing regimen specified for each age group (4 subjects from each of Cohorts 3 and 4 will contribute to this overall total). Thus a minimum of 24 subjects and a maximum of 40 subjects (assuming 2 adjustments per age group) may be enrolled in Part B.

Based on the results/conclusions of the interim analysis of the safety, PK, and antiviral data following the completion of Part B, there will be an option to enrol up to 120 subjects in Part C if the following conditions are met:

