##### **Part B and Part C:**

In Parts B and C, subjects will be randomised to treatment according to a central randomised list for each cohort. To protect the blind, the list will be produced by an unblinded biostatistician at Syneos Health who will be independent of the blinded statistician.

For Part B, subjects in Cohorts 3 and 4 will be randomised to RV521 or placebo (3:1). The randomisation list for Cohort 5 will be designed to ensure that the subjects who contribute to the final recruitment total of 24 are randomised to receive RV521 or placebo (2:1). The dose to be received by a given subject will be the dose currently being investigated at the time the subject is enrolled, in the applicable cohort, as described in Protocol Section 8.1.

For Part C Cohort 6, the randomisation list will be designed such that the total of approximately 120 subjects are randomised to receive RV521 or placebo (1:1).

This document is confidential.

Randomisation in Part C will be stratified by:

1. Duration of symptoms defined as the time first symptom reported by parent until randomisation, < 4 days or  $\geq 4$  days
2. Severity of illness, defined by the RSV Scoring <9 (mild-moderate) or  $\geq 9$  (severe)

At the time of randomisation, a subject will be sequentially assigned to the next available treatment from the randomisation list for that cohort. Randomisation will be performed using an interactive web response system. A blinded treatment kit (or > 1 kit, if required, in Part B), corresponding to the randomised treatment, will be allocated to each subject.

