## 6. General Aspects for Statistical Analysis

### 6.1. General Methods

- Unless otherwise specified, summaries for Part A will be presented by cohort, dose level and overall, summaries for Part B will be presented by cohort, treatment, dose level and overall, and summaries for Part C will be presented by treatment and overall.
- Unless otherwise specified, continuous variables will be summarised using the number of observations (n), mean, standard deviation (SD), median, minimum, and maximum. Means and medians will be presented with one more decimal than the observed values. SD values will be presented with 2 more decimals than the observed values.
- Unless otherwise stated, categorical variables will be summarised using number of observations (n), frequency and percentages of subjects.
- Presentations for PK data are described separately in Section 9. Presentations for PD data are described in Section 10.
- All relevant subject data will be included in listings. All subjects entered into the database will be included in subject data listings.
- All statistical testing will be 2-sided with an alpha level of 0.05, with no adjustment for multiple comparisons.
- For Part B, formal statistical testing will focus on the 24 subjects treated at the doses used in Cohort 5 that were identified in Cohorts 3 and 4. These 24 subjects comprise the whole of Cohort 5, plus the 4 subjects from each of Cohorts 3 and 4 that were randomized with the selected dose/placebo.
- Where there are multiple assessments at a given time point, only the results recorded on the scheduled time point page of the case report form (CRF) will be used for summarisation, unscheduled assessments will be listed only.

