### 8.1. RSV Clinical Scoring System Score

The RSV Clinical Scoring System gives a score from 0 to 12.

For each of Parts A, B and C, the RSV Clinical Scoring System score will be summarised at baseline and at each post-baseline time point. Summary statistics will be provided for the observed values and the corresponding changes from baseline for post-dose assessments. Plots of the mean  $\pm$  SD observed and change from baseline RSV Clinical Scoring System score by time point (baseline and each post-baseline assessment) will be presented. If necessary, lower SD bars will be truncated at 0 for the observed value plot.

For Part B, comparisons will be made between RV521 and placebo using a mixed effects analysis of covariance (ANCOVA) model on the change from baseline in RSV Clinical Scoring System score including a random effect term for subject, fixed effect terms for treatment group, age group ( $\geq 1$  month to  $< 6$  months or  $\geq 6$  months to  $\leq 36$  months at screening), visit and visit by treatment group interaction, and baseline RSV Clinical Scoring System score as a covariate. The model will be fitted to the 24 subjects treated at the final doses selected for Cohort 5 (see Section 6.1).

For Part C, comparisons will be made between RV521 and placebo using a mixed effects ANCOVA model on the change from baseline in RSV Clinical Scoring System score including a random effect term for subject, fixed effect terms for treatment group, visit, visit by treatment group interaction, duration of symptoms prior to randomisation and severity of illness at randomisation, and baseline RSV Clinical Scoring System score as a covariate.

For each model, a point estimate and 95% confidence interval will be calculated for the mean difference between RV521 and placebo.

Distributional assumptions underlying the statistical analyses will be assessed by visual inspection of residual plots. Normality will be examined by normal probability plots, while homogeneity of variance will be assessed by plotting the residuals against the predicted values for the model. If the distributional assumptions of a normal distribution in the parametric approach are not satisfied, investigations into influence of outliers or non-parametric methods will be considered.

In addition, for each of Parts A, B and C, the RSV Clinical Scoring System score will be categorised as:

- Mild – scores  $\leq 5$ .
- Moderate – scores  $> 5$  and  $< 9$ .
- Severe – scores  $\geq 9$ .

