### 10.2.1. Area Under the RSV Viral Load Curve

The DAVG statistic will be used to summarise the change in RSV viral load from baseline over a time period, standardised to a unit of time (sometimes called time weighted average change in RSV viral load), both for total RSV viral load by RT-qPCR and for RSV viral load by CBIA.

$$\text{The statistic is calculated as: } \text{DAVG} = \frac{\sum_{i=a}^b 0.5 (Y_{i+1} + Y_i) (t_{i+1} - t_i)}{t_b - t_a}$$

Where  $Y_i$  is the change from baseline in log10 RSV viral load at time point  $i$ ,  $t$  is the actual time at the specified time point,  $a$  is the baseline assessment at Dosing Visit 1, and  $b$  is the last assessment on Follow up Day 7.

If subjects have missing viral load data post baseline, then the data that are available will be used to generate the area under the curve (AUC) and will be divided through by the corresponding time period to obtain the DAVG value. Any subjects with less than 1 viral load value post baseline will be excluded from the DAVG calculation and hence from the analysis.

If baseline viral load are missing, an imputation method will be used under the assumption that the data are missing at random. The imputed value will be determined from an ANCOVA model with baseline viral load used as the dependent factor and duration of symptoms prior to randomisation, severity of illness at randomisation and age group ( $\geq 1$  month to  $< 6$  months or  $\geq 6$  months to  $\leq 36$  months at screening) as independent factors. The predicted value for the subject with the missing baseline value will be used as the imputed value.

DAVG for total RSV viral load by RT-qPCR and for RSV viral load by CBIA will be summarised (n, arithmetic mean, SD, CV, minimum, Q1, median, Q3, maximum, geometric mean, and geometric CV) by presence or absence of other known respiratory pathogens at baseline and overall for the mITT Population.

For Part B, comparisons will be made between RV521 and placebo using a mixed effects ANCOVA model on the DAVG including a random effect term for subject, fixed effect terms for treatment group, age group ( $\geq 1$  month to  $< 6$  months or  $\geq 6$  months to  $\leq 36$  months at screening) and presence or absence of other known respiratory pathogens at baseline, and baseline RSV viral load as a covariate. The model will be fitted to the 24 subjects treated at the final doses selected for Cohort 5 (see Section 6.1).

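### Part B models pool infants randomised 3:1 (Cohorts 3/4) with infants randomised in effect 10:6 (Cohort 5) without a cohort-stage term; about one eighth of any residual stage shift would enter the treatment difference (minor, cheap to fix)

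*SAP*

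**What the plan says.** Randomisation in Part B is by cohort, each with its own list (Protocol 8.5.4; SAP 3.8.1).

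- **Cohorts 3 and 4.** Protocol 8.5.4 states: "subjects in Cohorts 3 and 4 will be randomised to RV521 or placebo (3:1"). The SAP's description of Part B adds the unit: "Groups of 4 subjects will be randomised to receive RV521 or placebo (3:1) in Cohort 3 and Cohort 4, with enrolment occurring in parallel".
- **Cohort 5.** Its list is built so that "the subjects who contribute to the final recruitment total of 24 are randomised to receive RV521 or placebo (2:1"). The ratio is fixed for the combined 24, not for Cohort 5 itself.
- **Analysis set.** SAP 6.1 directs formal Part B testing at a pooled set: "These 24 subjects comprise the whole of Cohort 5, plus the 4 subjects from each of Cohorts 3 and 4". The Protocol synopsis is looser about who contributes: "The 4 subjects in the dose group that received the specified dose from each of Cohorts 3 and/or 4 will contribute to this overall total".
- **Order in time.** Within an age group the stages are sequential. The synopsis says that the older infants "can be enrolled in Cohort 5 after the completion of Cohort 3", and sets the matching rule for the younger ones and Cohort 4.
- **Models.** SAP 8.1 says of the clinical score: "The model will be fitted to the 24 subjects treated at the final doses selected for Cohort 5". Its terms are treatment, age group, visit, visit by treatment, baseline score and a random subject effect. SAP 8.2 analyses the parental scale in the same way. SAP 10.2.1 says the same of viral load: "The model will be fitted to the 24 subjects treated at the final doses selected for Cohort 5 (see Section 6.1"). The viral-load models in SAP 10.2.1 and 10.2.2 have treatment, age group, other respiratory pathogens, baseline viral load and a random subject effect.

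No Part B model contains cohort or stage. SAP 15 explains that dose was dropped because it coincides with age group, and does not mention cohort.

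**The concern.** When the allocation ratio changes between two randomised stages and the stages are pooled without a stage term, the arms hold different mixtures of early and late infants. Any stage difference that the other covariates do not explain is then partly read as a treatment difference. It also stays in the residual variance and widens the interval.

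Some drift is plausible. The protocol plans about 75 centres in both hemispheres and describes RSV as seasonal, with one type usually predominating in alternate years. Neither subtype nor symptom duration is in the Part B models, although symptom duration is in the Part C models.

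At stake are the estimates and intervals from the 24 infants on whom formal Part B testing is focused. Under Protocol 8.2, the Part B antiviral data are also part of the basis for starting Part C.

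**Working it through.** **Inputs.** Groups of 4 at 3:1 in Cohorts 3 and 4; 24 analysed at 2:1; planned Part B numbers of 16-28 on RV521 and 8-12 on placebo (Protocol 8.4.1, SAP 3.6.1); Part B powers of 69%, 87% and 96% for 2, 2.5 and 3 log with a 16/8 split (Protocol 11.2, SAP 3.7). The Part B SD is not given. I assume a range from 1.25 (the Part C planning SD) to 1.80 (back-solved below).

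**1. Allocation.**
- Two contributing groups of 4 at 3:1 give 6:2.
- 24 at 2:1 is 16:8.
- Cohort 5 is therefore (16 − 6):(8 − 2) = 10:6. The documents do not print this ratio.
- Check against the plan: four further groups for dose adjustments give 16 + 4×3 = 28 and 8 + 4×1 = 12. Both ends of the stated ranges are reproduced.

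**2. SD implied by the stated power.** For a two-sided two-sample t test at 0.05 with n = 16/8, setting power at 69% for 2 log gives SD 1.80. The three powers are then 69.0%, 86.6% and 95.7%, against the stated 69%, 87% and 96%. This shows that the three figures agree with each other; it does not verify the SD.

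**3. Size of the leak.** Let D be the early-minus-late shift in mean outcome left after the covariates.

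Bias = D × (early share in RV521 − early share in placebo) = D × (6/16 − 2/8) = 0.125 D.

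| Situation | Factor on D |
|---|---|
| Both cohorts contribute 4, Cohort 5 balanced on age, age in model | 0.125 |
| Uneven age splits of Cohort 5, age in model | about 0.08 to 0.14 |
| Only one of Cohorts 3/4 contributes (3:1 plus 13:7), unadjusted | 3/16 − 1/8 = 0.0625 |

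For D = 0.5, 1 and 2 log10 the bias at 0.125 is 0.06, 0.125 and 0.25 log10.

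**4. Bias in standard errors.** Variance factor without the stage term: 1/16 + 1/8 = 0.1875. The SE is 1.25 × √0.1875 = 0.54 or 1.80 × √0.1875 = 0.78. At D = 1 the bias is 0.125/0.54 = 0.23 SE or 0.125/0.78 = 0.16 SE.

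**5. Width of the interval at D = 1** (model with treatment and age group, Cohort 5 balanced on age).
- Variance factor with the stage term: 1/(6×2/8 + 10×6/16) = 1/5.25 = 0.1905.
- Without the term, the stage indicator leaves a residual sum of squares of 5.25 on 21 degrees of freedom, so the expected residual variance is SD² + 0.25 D².
- SD 1.25: √(0.1875 × 1.8125) = 0.583 without, √(0.1905 × 1.5625) = 0.546 with. Simulated mean SEs: 0.58 and 0.54.
- SD 1.80: √(0.1875 × 3.49) = 0.809 without, √(0.1905 × 3.24) = 0.786 with. Simulated mean SEs: 0.80 and 0.78.

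**6. Error rate and power** (40,000 simulated trials per setting, same model).
- Two-sided type I error without the term at D = 1: 4.2% (SD 1.25) and 4.4% (SD 1.80). With the term it is about 5%.
- Power at SD 1.80 with no stage shift, without and with the term: 69.2% and 67.7% at 2 log; 86.5% and 85.4% at 2.5 log; 95.6% and 95.3% at 3 log.
- Power at SD 1.80 for a 2 log effect with a 1 log shift: about 60% without the term if the shift masks the effect and 72% if it flatters it, against about 68% with the term.

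**The case against.** The strongest reply is that the term barely pays for itself. Mean squared error falls only if (0.125 D)² exceeds (0.1905 − 0.1875) × SD², that is, if D exceeds about 0.44 SD: 0.55 log10 at SD 1.25 and 0.79 log10 at SD 1.80. Below that, the point estimate is slightly less accurate with the term. This is correct, and it shows that the benefit is small. The possible loss is also small, about 1% in SE.

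Other replies stand as limits:

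- No passage gives or implies a stage shift in outcome. The 1 and 2 log10 values are illustrations, and 2 log10 equals the smallest treatment effect in the Part B power statement.
- The stage term is not a clean calendar split. Cohort 5 can open in one age group while Cohort 3 or 4 is still enrolling in the other.
- Part B is exploratory, its antiviral endpoints are secondary, its data are not combined with Part C, and summaries by cohort are planned. Those summaries may reveal a stage difference but do not remove it from the estimate.

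A reader might infer more than the documents support:

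- **That any difference between stages leaks.** It does not. Differences in age group and baseline (and pathogen status, for viral load) are adjusted for, and only about an eighth of the remainder enters the contrast.
- **That the Part B test is invalid.** In the simulations type I error stays below 5% under a shift, because the unmodelled shift also raises the residual variance.
- **That infants were selected into the 24 on viral response.** The DSMC review in Cohorts 3 and 4 is described as using safety and PK data, so the issue is drift over time.

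**Conclusion.** The point holds as a minor, inexpensive improvement. Stage is the unit in which infants were randomised and at which the ratio changed, and the Part B models omit it. The consequence is a bias of about one eighth of any residual stage shift and a somewhat wider interval, small beside the 2 to 3 log effects in the power statement.

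The one-eighth figure assumes that both cohorts contribute exactly 4 infants and that Cohort 5 is balanced on age; replacements and mITT exclusions would alter it. The SE and power figures rest on the assumed SDs of 1.25 and 1.80. For the clinical scales the same fraction applies to a shift in score points, but the documents give no SD from which to express it in standard errors.

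**What to change.** Add a fixed effect for cohort stage (Cohorts 3/4 versus Cohort 5) to the Part B models in SAP 8.1, 10.2.1 and 10.2.2, and state that it carries over to SAP 8.2. Protocol 11.1 allows a SAP amendment for Part B if it is signed off before database lock and unblinding of that part. State in the amendment that the term represents stage and not exact calendar time.

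The cost, if the stages do not differ, is one of about 20 residual degrees of freedom, roughly 1% in SE (√(0.1905/0.1875) = 1.008) and 1 to 1.5 points of power at 2 log.

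A sensitivity analysis in Cohort 5 alone is a weaker fallback, because it keeps only 16 infants: its variance factor is 1/10 + 1/6 = 0.267, against 0.1905 for the pooled model with the stage term.
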